7.2. Rescue Anti-Pruritic Medications

Rescue medications will be defined as those drugs, when used for the purpose of treating itch, that were required to be washed out prior to entry into TR03 as described in the protocol. For the purposes of this study, any ultraviolet (UV) light treatment received will also be defined as a rescue medication. If a medication is prescribed for chronic anti-pruritic use of greater than 2 weeks, the patient should be discontinued as described in the protocol.

Concomitant use of medications for pruritus is not prohibited except as described in the protocol. Details pertaining to the use of opiate medications are also discussed in the protocol. The list of protocol-defined rescue medications for itching is presented in [Table 1](#).

For drugs that may be used for multiple indications including pruritus, a drug is only considered a rescue medication if taken for pruritus. Use of rescue medications will not preclude continuation in the study; however, all uses of such medication along with their indication for use will be recorded. Patients will be provided a log on which to record use of rescue medications.

Table 1: List of Rescue Medications for Itching

Table 1: Rescue Medications for Itching		
Rescue Medication	Only intended for anti-pruritic treatment	Examples
Opioid receptor antagonists		naltrexone, naloxone
Antihistamines	✓	topical or systemic
Topical calcineurin inhibitors	✓	tacrolimus
Topical antibiotics	✓	---
Topical steroids	✓	---
Topical capsaicin	✓	---
Anti-septic baths and anti-septic cleansing lotions	✓	---
Anti-convulsant class drugs	✓	gabapentin or pregabalin
Systemic Steroids	✓	---
cyclosporin A and other immunosuppressants	✓	---
antidepressant medications	✓	paroxetine, fluvoxamine, amitriptyline
Malignant tumor related active treatment with a systemic drug	✓	---
UV Therapy	✓	---

The total number of rescue medications subsequent to the first dose of treatment with study medication and the number and percentage of patients using at least one rescue medication subsequent to the first dose of treatment with study medication will be summarized overall for the safety population.

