Incidence of concomitant rescue medication use will be summarized for the safety population. For incidence of use, patients will be counted only once within a medication category. In addition, for incidence of use calculations, if a patient reports taking the same medication more than once, as determined by WHO Drug name, then the medication will be counted only once (incidence of use) for that WHO Drug/medication name and patient.

The prevalence of use of rescue medications will also be summarized for rescue medications for the safety population. In this construct, multiple, distinct instances when a particular rescue medication was required will be counted as the number of times reported.

Antihistamine use across ATC classifications (a list to be furnished prior to data base lock) will also be summarized by incidence and prevalence for the safety population.

Rescue medication use will be presented separately in a data listing for the safety population.

The number and proportion of patients with rescue medication use at each visit and within ATC classification will be presented. This will be obtained by comparing the rescue medication onset date to the patient's visit dates and slotting the rescue medication accordingly. The number of days of rescue medication use will also be evaluated using descriptive statistics. Details regarding the analysis of number of days of rescue medication use are presented in Section [8.5](#).

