8.5. Rescue Medication Use

Details regarding the definition of and overall summary of rescue medications are presented in Section [7.2](#).

The number of days of use of rescue medications by study period (Pre-Treatment (after the date of last visit during the TR03 core study and prior to first dose during the TR03 extension study) and Treatment Period (Visits 2-14)) and by visit for the Treatment Period will be summarized

using descriptive statistics for both the overall number of days of use as well as for the number of days of rescue medication use for the drug classes presented in [Table 1](#).

The number of days of rescue medication use between each visit will be presented graphically for overall rescue medication use as well as for each of the drug classes presented in [Table 1](#).

The overall number of days of rescue medication use and number of days of rescue medication use for each of the drug classes presented in [Table 1](#) will be summarized using descriptive statistics. For patients with ≥ 1 day of rescue medication use, percentage of total time on study will be derived as: $[(\text{the number of days of rescue medication use})/(\text{days from the informed consent date through the fixed dose period})] * 100$. The mean for all patients on-study during the time period will be presented.

Time to first new use of rescue medication (days) will be summarized using descriptive statistics. The earliest date on or after the date of first dose of study medication on which a patient begins new rescue medication use will be considered the date of first new use of rescue medication. Time to first new rescue medication use will be derived as: $(\text{date of first new use of rescue medication} - \text{date of first dose of study medication}) + 1$. For patients who have no new rescue medication use on or after the date of their first dose of study medication time to first new use of rescue medication is not calculated.

It is recognized, however, that all of these evaluations are potentially confounded with early discontinuation that may or may not be observed among patients reporting use of rescue medications. That is, the extent and duration of use of rescue medications may, at least in part, be a function of duration of participation in the study.

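### Section 7.2 heads a by-visit table as rescue medication use but assigns records by onset date alone, so it counts starts and can miss continuing use

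*SAP*

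**What the plan says.** SAP section 7.2 plans several rescue summaries. One is by visit: "The number and proportion of patients with rescue medication use at each visit and within ATC classification will be presented". The next sentence fixes the derivation. It opens "This will be obtained by comparing the rescue medication onset date" and goes on to set that date against the patient's visit dates and slot the medication. Onset is the only medication date named. Neither 7.2 nor 8.5 gives a stop-date rule, an ongoing rule or a carry-forward for this table.

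On how use is captured, 7.2 says that patients receive a log and that "all uses of such medication along with their indication for use will be recorded". For its prevalence summary, "multiple, distinct instances when a particular rescue medication was required will be counted as the number of times reported". On course length, if a medication is "prescribed for chronic anti-pruritic use of greater than 2 weeks, the patient should be discontinued".

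Section 8.5 works with duration. Days of rescue use by study period "and by visit for the Treatment Period will be summarized", and "The number of days of rescue medication use between each visit will be presented graphically". It also defines a Pre-Treatment period, "after the date of last visit during the TR03 core study and prior to first dose during the TR03 extension study", so it provides for rescue use before the first extension dose.

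**The concern.** The heading speaks of patients using rescue at a visit, while the rule identifies patients whose record begins in the interval tied to that visit. The two agree only when no record crosses a visit. A patient whose continuous course straddles a visit was using rescue on both sides of it, but is counted on one side only. A patient who was already on rescue at first dose and continues has no onset in any treatment interval.

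This is the only planned by-visit percentage of patients using rescue. The incidence and prevalence summaries in 7.2 are not by visit, and 8.5 reports days rather than patients. A reader of the study report who wants to know what share of patients needed rescue in a given part of the year would go to this table and could read too low a figure. The same patient could show rescue days in an interval under 8.5 and no rescue use there under 7.2.

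**Working it through.** The SAP states no figure to reproduce. The check applies its rule to its own visit schedule.

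**Inputs from the SAP.** The visit weeks in section 7.3.3 are 1, 3, 5, 9, 13, 17, 21, 26, 30, 34, 38, 42 and 46, so most intervals last 4 weeks (L = 28 days). The nominal visit day is 7 × (week − 1) + 1. The 2-week limit on chronic anti-pruritic prescriptions in 7.2 makes courses of up to 14 days the relevant ones.

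**Assumptions, not in the SAP.** Each course is one continuous record of d = 7 or 14 days. Starts occur at random (Poisson) at a rate r of one per 56 or one per 28 days per patient.

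**Step 1: one course.** The Week 9 visit is nominal Day 7 × 8 + 1 = 57. A 14-day course from Day 50 to Day 63 has 7 days before that visit and 7 from it onward. The onset rule counts it in Weeks 5 to 9 only.

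**Step 2: share of course-intervals missed.** With evenly spread starts, a course is in use during an interval if it starts in the interval or in the d − 1 days before it. The onset rule misses the latter:

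(d − 1) / (L + d − 1)

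- d = 7: 6/34 = 17.6%
- d = 14: 13/41 = 31.7%
- d = 1 (daily records): 0/28 = 0%

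This is an upper bound for patients, because a repeat user may also start a new course in the same interval.

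**Step 3: share of users missed.**

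- Patients using rescue in the interval: U = 1 − exp(−r(L + d − 1))
- Patients with an onset in it: S = 1 − exp(−rL)
- Share of users missed: (U − S) / U

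| r | d | U | S | Missed |
|---|---|---|---|---|
| 1/56 | 7 | 1 − exp(−34/56) = 45.5% | 1 − exp(−28/56) = 39.3% | 13.5% |
| 1/56 | 14 | 1 − exp(−41/56) = 51.9% | 39.3% | 24.2% |
| 1/28 | 7 | 1 − exp(−34/28) = 70.3% | 1 − exp(−28/28) = 63.2% | 10.1% |
| 1/28 | 14 | 1 − exp(−41/28) = 76.9% | 63.2% | 17.8% |

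The share of users missed therefore runs from about 10% to 24%.

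**Step 4: pre-dose starts.** A course with onset in the Pre-Treatment period of 8.5 that continues past the first dose has its only onset before treatment. Under 7.2 it appears at no treatment visit, while 8.5 counts its treatment days. The model in step 3 does not cover this case separately.

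**The case against.** The strongest reply is that the loss depends on how records are built. Patients keep a log, all uses are to be recorded, and distinct instances are counted as often as reported. If each day or each single use becomes its own record, onset and use coincide and nothing is lost. This stands. A reader might infer that the table will certainly understate rescue use, but the SAP does not say how log entries become records.

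A second reply is that the rule is disclosed directly after the label, and that onset-based assignment is used elsewhere: sections 9.1.1 and 9.1.3 place an adverse event that is reported in more than one period in its earliest period of onset. That is so, but those are labelled as incidence calculations. Section 8.5 likewise speaks of new use when it means starts. The by-visit table in 7.2 makes no such distinction.

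Third, 8.5 recovers part of the information, since a course that crosses a visit adds its days to the later interval. The two sections also use different measures and classifications (patients by ATC class, days by Table 1 class), and nothing requires them to reconcile. Both points are fair, yet days of use do not yield the percentage of patients.

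Two further readings go beyond the documents. One is that very long courses make the loss much larger; the 2-week rule for chronic anti-pruritic prescriptions limits such courses, so they are a poor basis for sizing it. The other is that later percentages are further diluted by a whole-population denominator. Section 4.1 sets that denominator as the default unless otherwise specified, and it also refers to table shells, which are not shown and may specify another.

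**Conclusion.** The point holds in a conditional form. As written, the rule counts starts under a heading of use. Where a rescue record spans a visit, the patient drops out of the later interval unless another course starts there, and a continued pre-dose course is absent from all treatment visits.

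If records are continuous, roughly 10% to 24% of users in a 4-week interval are missed. That range rests on assumed course lengths of 7 to 14 days and assumed start rates of one per 28 to 56 days, none of which is in the SAP. With one record per day of use the loss is nil.

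Severity is minor. A reader might infer that the rescue endpoints are affected, but those in section 3.3.2 (time to first use and number of days of use) are derived in 8.5 and do not use this rule. The study plans no inferential statistics, and no decision depends on the table.

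**What to change.** In 7.2, replace the onset rule by an overlap rule: count a patient in a visit interval if any rescue record starts on or before the end of the interval and either stops on or after its start or is ongoing. This takes one sentence and the re-programming of one table, with the start and stop dates that the days-of-use summary in 8.5 already needs. The downside is that a long course appears in several intervals, so the visit counts no longer sum to the number of starts.

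If the onset rule is preferred, retitle the table *patients starting rescue medication, by visit*. That costs only a title change and makes the heading match the rule, but leaves no by-visit percentage of patients using rescue.

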7.3. Study Treatments

7.3.1. Study Drug Dosing

The number and percentage of patients reaching various achieved doses (30, 60, 90, 120, 150, 180 and 210 mg BID) will be summarized at each study visit beginning at the Visit 3/Week 5 study visit for the safety population. In addition, the number and percentage of patients will be presented for the highest dose achieved during the entire 50 weeks of active treatment.

Patient study drug dispensing/return and missed doses information will be presented in data listings for the safety population.

7.3.2. Extent of Exposure

Duration of exposure is defined as the total number of days a patient is exposed to any study drug and will be presented as the total number of days from the first dose date to the last dose date: (date of last dose of study medication - the date of first dose of study medication + 1). The date of first dose and date of last dose are reported in the eCRF on the dosing history and study completion pages, respectively. If the last dose date on the study completion page is missing, or if a patient is lost to follow-up, the visit date at which drug was last returned will be used as the date of last dose.

The duration of exposure to study drug will be summarized using descriptive statistics for the safety population.

Patient exposure information will be presented in a listing for the safety population.

It should be noted that duration of exposure calculated in this fashion does not account for missing individual doses or dosing interruptions as recorded in the eCRF.

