3.4. Treatments

Following enrollment, the patient will receive 30 mg open-label tablets. At each visit at which study drug is to be dispensed, enough drug should be supplied to ensure a sufficient number of tablets available for dosing until the next visit plus an additional 8 tablets to allow for visit windows and/or possibility of a missed visit.

Study drug can be taken with or without food. Patients will be instructed to take the AM and PM Study Drug tablets at the same times of the day, approximately 12 hours apart, preferably with 240 milliliters (mL) (approximately 8 ounces) of water. If the patient does not take a particular dose at the planned time he or she may take it up to 2 hours later. For example, if a patient is taking the Study Drug at 9 AM and 9 PM but forgets to take the 9 AM dose, the patient may take the 9 AM dose as late as 11 AM. After that time, the patient should skip the 9 AM dose and, instead, take the regularly scheduled next dose at 9 PM.

The first dosing day will be on either Visit 1a or Visit 1b. Titration will be based on tolerability. If the patient is experiencing a study-drug related AE or an AE that may be aggravated by study drug up-titration, the study drug dose should not be increased, regardless of the NRS score.

The Study Drug will be titrated during the Treatment Period Weeks 1 - 4, according to the schedule in Table 3 in the study protocol to a final dose of 30 mg BID up to 180 mg BID. The dosing for Treatment Week 1 is further described in Section 9.6.1 (Visit 1a) and Section 9.6.4 (Visit 1b) of the study protocol. Patients should only ever be dispensed a single strength of the study drug (e.g. 30 mg bottle(s) or 60 mg bottle(s)) at a visit.

Patients will titrate to tolerability beginning with a 30 mg dose on Day 1 (Visit 1a or Visit 1b) with a dose increase of 30 mg BID not more often than every 3 to 4 days in order to attain steady-state plasma concentrations of nalbuphine at each dose.

Patients should be instructed to up-titrate beginning with a single 30 mg dose in the evening (PM) and then begin dosing with an increased 30 mg BID dose the following day. Dose titrations should be maintained for 3-4 days before further up-titration of the patient's dose is attempted

The maximum dose the patient should reach at the end of Week 1 is 60 mg BID. If this dose is tolerated (as determined by the Telephone Contact 1 (TC1) assessment), an additional up-titration may be attempted during Week 2.

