7.3.3. Treatment Compliance

On the date of the first dose of study medication, the patient is expected to take only one dose (3 tablets) of study medication (in the evening). For the remainder of the study, patients should take two doses (6 tablets) of study medication each day (one in the morning and one in the evening).

At designated visits (i.e. Weeks 1, 3, 5, 9, 13, 17, 21, 26, 30, 34, 38, 42 and 46) patients will be distributed bottles containing study medication. Patients will return the bottles at a subsequent study visit, as instructed.

The number of tablets taken will be derived as: (total tablets dispensed across visits – total tablets returned across visits) and will be used to assess overall study compliance.

The total number of tablets planned will be derived as:
 $3 + (\text{number of days between day after first dosing day and last dosing day, inclusive}) * 6$.

Patient compliance over the entire time interval from first day of treatment until the last reported dosing date will be derived as: $(\text{number of tablets taken}/\text{number of tablets planned}) * 100\%$. Patient study compliance will be summarized using descriptive statistics overall for the safety population.

Patient compliance information will be presented in a data listing for the safety population.

8. Secondary Endpoint Analysis

Efficacy measurements will be evaluated as secondary endpoints in this study. The safety population will be used to evaluate the efficacy endpoints defined for this study. Eligibility for analysis of a particular endpoint will require only that the patient have a baseline value and at least one post-baseline value so that a change from baseline calculation can be obtained. All efficacy endpoints will be evaluated through the generation of descriptive summary statistics. For continuous variables, the mean, standard deviation, median, minimum, and maximum will be presented for a particular visit and for the change from baseline (Visit 1a or 1b). For categorical variables, the number and percentage of patients within each category of classification will be summarized by study visit. No formal statistical testing will be conducted.

Visit 1a or 1b will serve as the baseline visit for efficacy endpoints. Visit 1a will be the baseline for patients directly entering the Treatment Period as of Visit 1a and Visit 1b will be the baseline for patients entering the Treatment Period after participating in the Observation Period for any length of time.

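### When the final supply is not returned, tablets taken and tablets planned cover different time spans, so compliance is overstated for patients lost to follow-up

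*SAP*

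**What the plan says.** Section 7.3.2 defines exposure as "date of last dose of study medication - the date of first dose of study medication + 1". The last-dose date normally comes from the study completion page. If that date is missing, or if the patient is lost to follow-up, "the visit date at which drug was last returned will be used as the date of last dose". The two conditions are joined by *or*, so as worded the rule also replaces a recorded date for a lost patient.

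Section 7.3.3 takes tablets taken as "total tablets dispensed across visits – total tablets returned across visits". Tablets planned are 3 plus 6 times the "number of days between day after first dosing day and last dosing day, inclusive". Compliance is the ratio of the two, over the interval "from first day of treatment until the last reported dosing date". Bottles are dispensed at Weeks 1, 3, 5, 9, 13, 17, 21, 26, 30, 34, 38, 42 and 46 and come back at a later visit. Section 3.4 sizes each supply: "enough drug should be supplied to ensure a sufficient number of tablets available for dosing until the next visit plus an additional 8 tablets". No rule covers a bottle that never comes back.

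**The concern.** A patient who is later lost will typically hand in the old bottle at the last attended visit and leave with a new one. Section 7.3.2 treats that patient as having taken nothing after the visit. Section 7.3.3 treats the same patient as having swallowed the whole new bottle, spare tablets included. Both cannot be true, and the ratio mixes them.

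At stake is the compliance summary, which reports the mean, SD and maximum as well as the median. The error always raises compliance, and it falls on the patients whose drug-taking is least known. The last-dose date also sets the length of exposure. Section 8.6 uses it as the date of discontinuation during the Treatment Period. It may also affect the subsets with at least 6 or 9 months of treatment in Sections 8.1.3, 8.1.5 and 8.1.8, if treatment time there is taken from Section 7.3.2; the SAP does not say.

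**Working it through.** The SAP gives no compliance or exposure figure to reproduce, so its own rules are applied.

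**Inputs.** 3 tablets on day 1 and 6 per day after that, and the dispensing weeks (Section 7.3.3); 8 spare tablets per supply (Section 3.4); last dose set to the last-return visit (Section 7.3.2). Assumed: visits fall on schedule, and the patient returns the old bottle at the visit, receives the new one and is then lost.

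**Formulas.**
- Visit day L = 7 × (week − 1) + 1
- Planned = 3 + 6 × (L − 1)
- New supply = 6 × (days to next visit) + 8
- Compliance = (tablets used from earlier bottles + new supply) / planned

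**Week 3 in full.** L = 15 and planned = 3 + 6 × 14 = 87. Dispensed at Week 1: 3 + 6 × 13 + 8 = 89. Dispensed at Week 3: 6 × 14 + 8 = 92. What comes back depends on which visit-day doses came from the old bottle:
- none (8 tablets returned): (89 + 92 − 8)/87 = 173/87 = 198.9%
- the morning dose (5 returned): 176/87 = 202.3%
- both doses (2 returned): 179/87 = 205.7%

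**Fully adherent patient, by last visit attended.** The range runs from no visit-day dose to both visit-day doses taken from the old bottle.

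| Lost after | L | Planned | New supply | Compliance |
|---|---|---|---|---|
| Week 3 | 15 | 87 | 92 | 198.9-205.7% |
| Week 5 | 29 | 171 | 176 | 199.4-202.9% |
| Week 9 | 57 | 339 | 176 | 150.1-151.9% |
| Week 13 | 85 | 507 | 176 | 133.5-134.7% |
| Week 26 | 176 | 1053 | 176 | 116.1-116.7% |
| Week 46, supply for 28 days | 316 | 1893 | 176 | 109.0-109.3% |
| Week 46, supply for 35 days | 316 | 1893 | 218 | 111.2-111.5% |

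The last supply is shown for both 28 and 35 days because the interval depends on when the End of Treatment visit falls.

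**Masking.** Take a patient who used 75% of planned tablets. Lost after Week 17 (planned 675): (0.75 × 675 + 176)/675 = 682.25/675 = 101.1%. Lost after Week 5: (0.75 × 171 + 176)/171 = 304.25/171 = 177.9%.

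**Skipped return.** If the Week 3 bottle is not returned at Week 5 either, the last return is on day 15: (81 + 92 + 176)/87 = 349/87 = 401%.

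**Exposure.** If the patient in fact dosed up to the day before the next visit, the shortfall is 28 − 15 = 13 days (Week 3), 56 − 29 = 27 days (Week 5) or 175 − 141 = 34 days (Week 21). It is slightly more if spare tablets were used, and more again if a return was skipped.

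**Matched spans.** Counting only returned bottles, with both counts running to the day before the visit, gives 81/81 = 100% (Week 3) and 165/165 = 100% (Week 5). Leaving the visit day in the denominator alone would give 81/87 = 93.1% and 165/171 = 96.5%.

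**The case against.** The strongest objection is that Section 7.3.3 does not import the fallback. It speaks of the last *reported* dosing date, and the last-return rule is written for exposure. Read literally, a lost patient with a recorded date has planned tablets counted up to that date. This stands as a point about wording: the link is the natural reading, not an explicit one. It does not rescue the plan. A patient with no recorded date would then have no defined compliance. One with a recorded date would still carry the unreturned bottle in the numerator.

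The reach is also narrow. Patients who stop drug are asked to attend the End of Treatment visit (Sections 3.2.1 and 3.2.2), so only those truly lost or with a missing date are affected. Dispensing, return and compliance data are listed, so extreme values would be seen. No population or test depends on compliance. All of this stands and limits the weight of the point.

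Three stronger readings are tempting, and the SAP supports none of them:
- **That lost patients score above 200% in general.** Short of a skipped return, this needs loss right after Week 3 or Week 5, and even there the figure is just under 200% if dosing from the old bottle ended the day before. These percentages also rest on the SAP's fixed 6 tablets per day. That conflicts with the titration and dose range in Section 3.4, and the two must be reconciled separately. The mismatch of spans remains whatever the tablet count; the exact percentages do not.
- **That exposure is understated for these patients.** This is so only if dosing continued after the last return, which is unknown. Ending exposure at the last accounted-for visit is a defensible convention when no date is recorded.
- **That the safety results are compromised.** Adverse event percentages use the number of patients in the safety population, and no exposure-adjusted rate is planned.

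**Conclusion.** The point holds as a defect in the compliance derivation. Followed on its natural reading, the SAP overstates compliance for any patient whose final supply is not returned and whose last dose is set to the last-return visit. The excess is roughly a doubling after Week 3 or Week 5, about half after Week 9, and about a tenth by Week 46. This assumes scheduled visits, 6 tablets per day and a full new supply. Partial non-adherence can be masked, most plausibly at mid-study losses, where the result lands near 100%.

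The effect on exposure is conditional: at most about one dispensing interval (13, 27 or 34 days, apart from spare tablets or a skipped return), and nil if the patient stopped at the visit. A patient with no recorded last-dose date who never returned drug has no last-dose date at all. The number of patients concerned cannot be judged from the SAP, and only descriptive summaries are affected. It should be corrected before the tables are programmed.

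**What to change.** **Section 7.3.3.** When a final supply is not returned, compute tablets taken and tablets planned over the same span: first dose to the last visit with a recorded return, ending the day before that visit or using one visit-day convention for both counts. Exclude the unreturned supply from the numerator whatever last-dose date is recorded. It is not enough to drop only supply dispensed on or after the last-dose date. With loss after Week 5 and a recorded last dose on day 32, the day-29 bottle would stay in: (171 + 176)/(3 + 6 × 31) = 347/189 = 184%. Align the wording on the last reported dosing date with Section 7.3.2, and report the number of patients with unreturned supply.

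**Section 7.3.2.** Use a recorded last-dose date whenever one exists, including for patients lost to follow-up. Use the last-return visit only when the date is missing, and state a fallback for patients who never returned drug.

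**Cost.** A few sentences of SAP text and a few lines of code, using dispensing and return data that the SAP already lists. The downside is that, for affected patients, compliance no longer covers the period after the last return.
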